# (2) Shipping of Blood Samples:

Return plasma samples every two months to the central laboratory. Return the BLACK TOP quality control tubes with them. All tubes are packed in the styrofoam shipping container provided with 5 lbs of dry ice and handed to the carrier for air delivery. (We suggest that you retain the container sent by the lab.) Avoid shipping on Friday. For shipment from Canada, use 10 lbs (4.5 kilos) of dry ice in the container and avoid shipping on Thursday or Friday. For shipment from Belgium, use 15 lbs (7 kilos) of dry ice in the container and avoid shipping on Wednesday, Thursday, or Friday. Please contact the central laboratory prior to shipping the samples. The catecholamine reference sample has been assayed by the central laboratory prior to being distributed. When returned, these samples will be reassayed to check for stability during storage of the samples at the clinical center and during transport by the carrier (quality control).

Flow Chart for Collection of Blood Samples

II. Echocardiograms

To qualify for the Registry Substudy, the echocardiogram must be of good quality. To be judged as good quality, an echocardiographic study must have the following:

- (1) Adequate display of the aortic and mitral valve in the parasternal long axis view with minimal or no anterior angulation of LV apex.
- (2) Adequate endocardial definition of both visualized LV walls in the parasternal long axis and apical view.
- (3) Adequate endocardial definition of anterior septum and posterior wall in the short axis view with a circular appearance of the LV cavity at mid-papillary and mitral valve level.
- (4) Adequate M-mode scan from LV at mid-papillary level to aortic root.

The following recording procedures will be followed.

a. Parasternal window

(1) Obtain a parasternal long axis view that shows good endocardial definition of septum and posterior walls, good visualization of mitral and aortic value as well as proximal aortic root. The view should be obtained from the intercostal space that places the LV long axis as perpendicular to the sound beam as possible. This location should be recorded for future serial studies.

(2) Obtain a parasternal short axis view at mitral valve and papillary muscles levels by rotating transducer from the long axis view. When properly angulated, the short axis view should show a circular or near circular geometry of the LV. Record an M-mode scan of the LV at papillary level gradually moving up the mitral valve and into the aortic value insuring that the M-mode cursor runs through the center of the LV cavity.

b. Apical window

(1) Obtain an apical four chamber view with the transducer as far laterally as possible to maximize size of the LV cavity and provide good visualization of mitral valve. Rotate towards the two-chamber view again insuring adequate angulation to maximize size of LV cavity.

NOTE: The following Doppler procedures are to be done only by hospitals participating in the SOLVD Echocardiography Substudy.

(2) Doppler

(a) Mitral inflow - apical four chamber view, place a 0.5-1 cm sample volume at the mitral anulus level so that during diastole it falls at the entrance at a sweep speed of 100 mm/sec.

(b) Aortic anulus (LV outflow) - apical long axis view. Place sample volume at the level of aortic anulus just proximal to aortic valve and record a minimum of 210 cardiac cycles at a sweep speed of 100 mm/sec.

(c) Direct the continuous wave (CW) beam into the ascending aorta and record 10 or more cycles after careful angulation to obtain the highest aortic peak velocity possible.

## (3) Other Doppler recordings

(a) Search for mitral, aortic and tricuspid regurgitation with pulsed and CW Doppler using standard techniques. When regurgitant lesions are present, record the regurgitant jet with SW from the window providing the highest jet velocity.

(b) Ascending aorta velocity using CW Doppler from the suprasternal window.

# Measurement and calculation

The original copy of the echocardiogram tapes will be sent to Dr. [name]' laboratory in Houston for evaluation. All SOLVD patients will be studied on designated SOLVD tapes. Copies of each of the studies can be kept at the individual SOLVD center to be used locally (i.e., reports to the referring M.D.) and as backup in case the original tapes should be lost in transit.

# Procedures for quality control

The quality of echocardiographic studies will be judged at the core laboratory as excellent, adequate or suboptimal for measurements. Centers with one or more suboptimal studies during the first 5 patients will be contacted directly by the director of the core laboratory to re-address the criteria to be used locally for quality judgment. The other participating centers will absorb in equal distribution the additional recruitment load.

#### III. Holter Monitoring

# (1) Technique Procedures

Standardization of the ambulatory recording devices is mandatory. For each center, the ambulatory ECG recording devices should be able to produce a high quality ECG signal which include the following requirements:

(a) All recordings must have a standard calibration signal of lmV (10mm) pulses over at least 8 minutes in duration for S-T analysis.

(b) A standard patient preparation utilizing a degreasing and an abrasive scrub to reduce surface impedance. (This will require an inservice with the clinic coordinators of the participating centers.)

(c) Recorders must be dual channel reel-to-reel or PR 3XST cassette recorders with frequency responses of .05-100 Hz with lead placement at CM5 and CM1 to allow for the detection of both ischemic events and ventricular arrhythmias. At the time of initial lead placement, alternative leads may be selected (by a predetermined algorithm) if R-wave amplitude is insufficient or evidence of MI or other factors would preclude S-T segment analysis.

(d) Test strips for signal quality will be an absolute requirement so that an adequate signal is obtained in all cases. Each center will need a test oscilloscope with a strip recorder or a single channel ECG machine for testing signal quality in each patient. Standardization pulses can be produced either by recorders with internal calibrators or through a separate pulse generator box plugged into the recorder.

#### (2) Procedures for Quality Control

Quality control procedures for ambulatory electrocardiographic recordings will involve three phases. Phase I will address application techniques, Phase II ambulatory ECG equipment requirements, and Phase II ambulatory ECG tape analysis.

# Phase I

This phase includes instructions to all participating centers on electrode application and skin preparation involving rigid criteria for cleaning the skin, position of electrodes at V1 and V5 positions and the application of the disposable electrodes on the skin. It is imperative that the skin be properly prepared to reduce skin impedance (3800-5000 ohms) and the site of the electrode placement be carefully chosen to eliminate the presence of artifacts and wandering baseline on the ECG recording. Electrodes should be applied on top of the bone and not on muscle or fat tissue to reduce artifacts (a detailed electrode application procedure will be included). The electrodes and lead wires should be secured with micropore tape and the use of stress loops. All ambulatory ECG recordings will be graded for tracing quality.

# Phase II

All recording should be performed using AM ambulatory ECG recording devices or a comparable cardio cassette recorded with a flat frequency response of 0.05 to 100 Hz. Most manufacturers of Holter recorders would be consdered acceptable for arrhythmia documentation and S-T segment analysis except for the Oxford AM recorder which does not have an acceptable frequency response. The recording tapes should be black oxide 2.65 inches in diameter and all recorders should operate on 9V disposable batteries. The Cardio Data PR 2XST cassette recorder would be the preferred system to replace the reel-to-reel recorder since it is specifically designed to be run with the Cardio Data ST analysis software program. A standard tape calibration signal will be required for a minimum of 8 minutes on each patient. This involves a series of 1 mV calibration standards fed into the ambulatory ECG recorder for 8 minutes by an external pulse generator box or provided by recorders with internal calibrators. The Cardio Data PR 3XST cassette is equipped with an internal 8 minute calibration signal. The calibration signal would be followed by 15 seconds of ECG test strips to test for quality of the electrical signal being recorded. This requires a standard single channel 12-lead ECG machine or an oscilloscope with a strip recorder and a test cable. While obtaining the strip, the electrodes should be tapped gently to ensure the absence of artifact and baseline wander. A minimum of 5 mm amplitude at a gain of 1mV is needed on both channels. A six second segment must be sent with each tape to be scanned. (Instructions for test completion and removal of tape will be covered.)

#### Inservice and Training

Training sessions will be set up to cover Phases I and II for each

participating center. An instruction book with the proper steps for application of electrodes and proper ambulatory ECG recording technique will be provided. This training session should be performed at the investigators' meeting. Equipment maintenance will also be reviewed as it is important to ensure proper equipment functioning. All participating centers will be required to follow standard cleaning instructions for the external recorder surface, leadwires and the recording head. After 8 to 10 uses, each recording head should be demagnetized to ensure reliable recordings. Cables and lead wires will be checked for fraying and broken connections and discarded if warranted.

#### Supplies

All participating centers will be supplied with recording kits from the Core Lab consisting of 5 electrodes, 1 9V battery, gauze sponges, razor and reel-to-reel tape (or cassette tape) mailing labels. Additional supplies would be sent in bulk, such as preparation solution (Freon), prep pens for skin abrasion, micropore adhesive tape and cleaning solution for the ambulatory ECG recording head.

# Phase III - Ambulatory ECG Analysis

Ambulatory ECG analysis will be performed on the Cardio Data MK4 Scanning System with an S-T analysis software program. After each tape is received it will be scanned and the results transmitted to the Coordinating Center. Quality control of the scanning system to test the reproducibility and accuracy of the MK4 will be carried out monthly and whenever the research scanner detects a malfunction of the system. This involves running a tape with known quantity of arrhythmia. Quality control of the research scanner will be performed on 2% of all recordings submitted in a random fashion from the Coordinating Center. The selected tape will be read by the quality control coordinator. If a discrepancy of greater than 10% occurs, the quality control coordinator will determine the cause and reduce the variability appropriately. Analysis of QC will be stored at the Coordinating Center. A hand count comparison will be performed on 1% of all submitted recordings. All reports will be reviewed by the staff cardiologist or his designee to confirm the ECG interpretation. Ten percent of these reports will be read blindly be a second cardiologist to quality control the interpretations. Since the appropriate quality control of tapes for silent S-T shifts is not well defined, the ambulatory monitoring laboratory at the University of Florida (Gainesville) under the supervision of [name] will randomly re-read 5% of the tapes for S-T segment quantitation.

### S-T Segment Analysis

All S-T segment analysis will be performed utilizing the MK4 S-T analysis software program. To perform S-T segment analysis, eight minutes of 1mV calibration signals must be present on the analog or cassette tape to be scanned. The technician sets two S-T markers; one at the isoelectric baseline and one at the J point. A third measurement is made at .06 seconds to the right of the J point. Once set, a minute-by-minute trend will be compiled for all minutes containing valid measurements. For the data to be used, there must be at least sixteen beats retained in every minute.

#### Mailing and Storage of Tapes

All participating substudy centers will be required to label and mail all accumulated tapes to the Core Lab on a weekly basis. The scanning center will be responsible to log all tapes received per center, including patient name (study initials and ID), date of ambulatory ECG recording, and date of birth. The ambulatory ECG recorder and cable number will be included on the mailing sticker so a technical difficulty can be quickly identified. All tapes will be stored in an environment with low humidity and protected from ultraviolet light.

#### IV. Six-minute Walking Test

The patient is to take nothing by mouth except for clear liquids for at least four hours prior to the test. Daily cardiovascular medications may be given four hours prior to the test or held until after the test. Patients should be advised not to smoke for at least two hours prior to exercise. The walking test is to be conducted in an enclosed corridor on a course 100 feet (approx. 30.5 meters) long. The corridor should not be heavily transited and should be free of obstacles and distractions. It should be divided into taped five-foot sections to allow easy measurement of the distance walked. Chairs are to be placed at either end of the course so that patients may rest when needed.

Patients are to be instructed to walk from end to end for six minutes, covering as much distance as possible. During the six minutes they may rest whenever necessary. However, patients should be encouraged to exercise to the point of exhaustion and should only terminate the walk prior to six minutes if severe shortness of breath, muscular pain, dizziness or anginal symptoms should develop. In order to standardize the test, encouragement is offered during the walk. Every thirty seconds while facing the participant, one of the following two phrases is delivered: "You're doing well" or "Keep up the good work." Instructions are given to the patient as outlined below and immediately prior to the start of exercise a marker is placed on the Holter tape. At the end of six minutes, the patient is directed to stop, a marker is placed on the Holter tape and the distance walked to the nearest foot (or meter) is recorded.

The following instructions are to be read verbatim to the patient:

The purpose of this test is to determine how far you can walk in six minutes. You will start here and go to the chair at the end of the hall, turn around, and walk back. After arriving back at the starting point, you will go back and forth again. Go back and forth as many times as you can in the six-minute period. If necessary, stop and rest and stay there until you can start again. However, the most important thing about the test is that you cover as much distance as possible during the six-minute period.

I will let you know when the six minutes are up. When I say STOP, please stand right where you are.

Do you have any questions about the test? Please explain to me what you are going to do. Are you ready? Start when I say "GO."

# Appendix D STRATIFICATION FOR SUBSTUDY PARTICIPANTS

It is expected that the vast majority of the participants eligible for the SOLVD Registry will have ischemic or hypertensive heart disease, and that about 5-10% would have cardiomyopathies or other "rare" etiologies. Thus, of the 6000 expected participants for the Registry, approximately 300-600 participants would be of the "rare" etiologies, and 5400-5700 would be of the more common etiologies.

The Registry has the potential to provide valuable clinical history information on the so-called "rare birds" of congestive heart failure. Given the interest in obtaining complete and detailed baseline information on these patients, the computer program for identifying those patients to be included in the Registry Substudy will essentially sample the Registry participants with two different sampling proportions: 100% of the rare etiologies would be included in the Substudy, and somewhere around 7-13% (approximately 400-700 participants) of the ischemic heart disease participants would be included in the Substudy, to roughly complete the 1000 patient desired.

Essentially, the Substudy subsample is a stratified random sample of the Registry sample, with two strata (ischemic heart disease, other) with different sampling proportions (.07-.13, 1.00, respectively).

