## VI. STUDY SIZE

It is expected that over 6,000 patients will be recruited into the Registry during the specified nine-month time period. In order to avoid a predominance of ischemic heart disease, special attempts to include patients with other etiologies may be required. These categories include the following:

- 1) Valvular heart disease with EF  $\leq$  45%
- 2) Primary diagnoses of idiopathic cardiomyopathy and active myocarditis.

3) Unusual and specific causes, such as amyloidosis, hemochromatosis, hypertrophic hyperdynamic cardiomyopathy (so-called IHSS), diabetic cardiomyopathy, alcoholic cardiomyopathy, etc.

The period for collecting such unusual cases may be extended beyond the first nine months Registry collection and as long as 1991. A decision regarding that will be made after the first nine months of recruitment.

The calculations in Table 1 examine the statistical power attained for comparing the mortality rates between two subgroups from the 6000 SOLVD Registry patients, under various assumptions. Comparisons of mortality rates can be done asymptotically with the test of difference of two binomial proportions (Rosner, p. 325). A two-sided test with a 0.05 level of significance is thus considered.

The following examples aid in the interpretation of the calculations in Table 1.

Case 1 would be for testing the difference in mortality between, for example, those with EF ≤ .40 (75% of Registry) vs. those with EF > .40 (25% of Registry). Power for this case is virtually unity.

Cases 2-3 and 4-6 look at testing the different mortality rates in a very rare subgroup vs. the entire rest of the Registry, under different relative risk situations. The rarer the etiology, the higher the relative risk needs to be, but a RR of 2 or greater has sufficient power to be detected, even after only one year. The power is greatly improved after three years.

Cases 7-9 look at testing the different mortality rates between two very rare subgroups, one that is seen in 2% of the patients vs. one that is seen in 1% of the patients. Informal estimates of prevalence of different etiologies suggest that amyloidosis would be seen in 20 per 1000 patients (2%), hemochromatosis would be seen in 10 patients per 1000 (1%), diabetic cardiomyopathy in 6-8%, alcoholic cardiomyopathy in 7-10%, post-partum in 2%. These cases need three years' worth of data to be tested with reasonable power, even with a relative risk of 2.

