Cases 10-11: With 6000 persons in the Registry, it is not unreasonable to expect roughly 1000 patients with idiopathic cardiomyopathies. If this group is divided by tertiles of EF into low, intermediate and high EF, one would like to compare the mortalities between the high EF group and the low EF group. Assuming a relative risk of 3 provides power close to 1, while with a relative risk of 2, the power is virtually one at the three-year comparison.

				One-ye	ear		Power
Case #	n	m	pl	p2	RR	@1-year	@3-year
1	4500	1500	.12	.05	1/2.4	1.00	1.00
2	5900	100	.12	.24	2.0	.90	1.00
3	5900	100	.12	.18	1.5	.45	.77
4	5950	50	.12	.24	2.0	.69	.94
5	5950	50	.12	.30	2.5	.86	1.00
6	5950	50	.12	. 36	3.0	.99	1.00
7	120	60	.20	.30	1.5	.33	.58
8	120	60	.20	.40	2.0	.81	.97
9	120	60	.12	.24	2.0	.54	.87
10	333	333	.05	.15	3.0	.99	1.00
11	333	333	.06	.12	2.0	.77	.99

Table 1 One-year and three-year power for comparison of mortality rate between various Registry subgroups

Key: n = sample size in first subgroup m = sample size in second subgroup pl = 1-year mortality rate in first subgroup p2 = 1-year mortality rate in second subgroup RR = relative risk of second to first subgroup Thus, it is clear from the above examples that a sample size of 6000 patients in the Registry is quite adequate for comparison of mortality rates between various subgroups, especially after three years but in several cases even after one year.

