# VII. DETAILED INVESTIGATIONS IN A SUBSAMPLE OF 1000 PATIENTS (REGISTRY SUBSTUDY)

Since there is no uniform requirement of investigations other than ejection fraction or chest X-ray in the Registry, it is possible that some of the data collected from the hospital records may be biased (e.g., more tests done on the "sickest" patients). In order to obtain key data on a relatively "unselected population" that differs from the Trials substudy population and to assess the biases inherent in the main body of the Registry, 1000 stratified (see appendix D) randomly chosen patients will be studied. The following procedures are to be completed:

- M-mode and 2-D echocardiograms (to be read centrally). Doppler i) echocardiograms would be performed only at those centers participating in the SOLVD Echocardiography Substudy.
- Physical examination and history. ii)
- Drawing of blood for plasma renin and catecholamines iii) (determinations to be performed centrally).
- Seventy-minute ambulatory Holter monitoring (one hour at rest, iv) during the 6-minute walking test, and for 3 minutes post walking) (to be read centrally).
- Six-minute walking test. v)
- Chest X-ray and electrocardiogram, if not done within 90 days. vi)

Once a patient has entered the Registry, the SOLVD microcomputer data entry system will identify whether a particular patient is to be selected for the Registry Substudy. Once such a patient is identified, he/she is invited to participate in the Registry Substudy. If he/she consents and a good quality (as defined in Appendix C) echocardiogram is obtained, all the other tests are performed. If he/she refuses or a good quality echo cannot be obtained, this patient does not enter the substudy but should still be included in the main Registry. The flowchart in appendix A2 describes the procedure for the Registry Substudy clinic visit. Preferably, the visit is to be scheduled for the day the echocardiogram can be performed. If this is not possible, the echo and the rest of the procedures must be done within two weeks of each other and any major intercurrent events occurring must be documented with a Hospitalization form. The clinic visit should take place no later than 90 days after enrollment.

A brief description of each procedure follows; for details on their protocols, see Appendix C.

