### IX. DATA COLLECTION

Registry data will be collected in consecutive patients screened at the participating clinical centers who meet the Registry entry criteria. These will include patients who enter the randomized trials during the accession period to the Registry. The inclusion and exclusion criteria for patients entering the Registry have been previously defined. The participating centers have been described in Section III. The period of enrollment into the SOLVD Registry has been described in Section VIII.

Each clinical center will be expected to enroll at least 300 patients into the Registry, including a subset already being enrolled in the SOLVD trials. In addition, approximately 50 stratified randomly selected patients at each center will undergo additional baseline testing, including an M-mode and two-dimensional echocardiogram, a 70-minute Holter monitoring, and a 6-minute walking exercise test. These patients, aggregated over all centers to form the substudy sample, will be stratified according to the etiology of the underlying condition, to include ischemic and/or hypertensive heart disease, patients with idiopathic cardiomyopathy, and "valvular" myopathy. Attention will be specifically directed to a subset with the entry syndrome of pulmonary edema without acute MI.

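### Section VI expects about 1000 idiopathic cardiomyopathies, but Appendix D sizes the Substudy on 300-600 patients with any rare etiology; both cannot hold

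*Protocol*

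**What the plan says.** Section VII sets the Substudy target: "1000 stratified (see appendix D) randomly chosen patients will be studied". Section IX gives the load: "approximately 50 stratified randomly selected patients at each center will undergo additional baseline testing".

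Appendix D builds the 1000 from two strata. It expects that "about 5-10% would have cardiomyopathies or other" rare etiologies, which it converts to 300-600 of 6000 patients, with 5400-5700 in the common group. The selection program then takes "100% of the rare etiologies would be included in the Substudy, and somewhere around 7-13% (approximately 400-700 participants") of the ischemic patients.

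Section VI works from the same Registry size ("It is expected that over 6,000 patients will be recruited into the Registry"). For Cases 10-11 of Table 1 it states that "it is not unreasonable to expect roughly 1000 patients with idiopathic cardiomyopathies". These are split into EF tertiles of 333, and the top and bottom tertiles are compared. The same section gives informal estimates of other etiologies: amyloidosis 2%, hemochromatosis 1%, and "diabetic cardiomyopathy in 6-8%, alcoholic cardiomyopathy in 7-10%, post-partum in 2" per cent.

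**The concern.** Idiopathic cardiomyopathy is a cardiomyopathy, so in Appendix D it belongs to the stratum sampled in full. Section VI's count of that one disease is larger than Appendix D's upper limit for the whole stratum. Each count carries a design decision: the sampling fractions in the selection program, and the stated power of two of the eleven cases in Table 1.

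If the larger count is right, the Substudy loses its ischemic sample or runs well past 1000. Section VII wants the Substudy partly to assess bias in the main Registry, most of which is expected to be ischemic or hypertensive. If the smaller count is right, the protocol promises power for the idiopathic tertile comparison that it will not have at one year.

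**Working it through.** **1. Appendix D agrees with itself.** The common-stratum fraction is (1000 − rare) / (6000 − rare).
- 300 rare: 700 / 5700 = 12.3%
- 600 rare: 400 / 5400 = 7.4%

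This matches the stated 7-13% and 400-700 patients. The fault shows only against Section VI.

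**2. The two counts.** Section VI: 1000 / 6000 = 16.7% for idiopathic disease alone. Appendix D: at most 10% (600) for all rare etiologies together.

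**3. If Section VI is right.** Idiopathic cases at 100% give 1000 selections, the whole Substudy. Adding 7-13% of the other 5000 (350-650) gives 1350-1650.

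An upper figure comes from adding the specific etiologies, on the assumption that none overlap:
- low: 2 + 1 + 6 + 7 + 2 = 18%, or 1080 patients; with idiopathic, 2080
- high: 2 + 1 + 8 + 10 + 2 = 23%, or 1380 patients; with idiopathic, 2380

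With the 20 centers that Section III uses as an example, that is 104-119 rare-stratum selections per center (2080/20 and 2380/20), against about 50 planned. These are selections, before refusals, poor echocardiograms and inability to attend.

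**4. If Appendix D is right.** Even if every rare patient were idiopathic, each tertile would hold 300/3 = 100 to 600/3 = 200 patients.

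Power for two equal groups of n, two-sided 0.05, with p̄ the mean of p1 and p2:

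Φ{ [ |p1 − p2| − 1.96 √(2p̄(1 − p̄)/n) ] / √[ (p1(1 − p1) + p2(1 − p2))/n ] }

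Check on Case 11 as stated (n = 333, .06 vs .12): (.06 − .0435)/.0221 = .75, so power is .773, against .77 in Table 1.

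Same case at n = 100: (.06 − .0793)/.0402 = −.48, so power is .316.

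Table 1 gives no three-year mortality rates. I assume 1 − (1 − p)³: .143 vs .386 for Case 10, and .169 vs .319 for Case 11.

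| | Table 1 | n = 333 | n = 200 | n = 100 |
|---|---|---|---|---|
| Case 10, 1 year | .99 | .991 | .918 | .656 |
| Case 10, 3 years | 1.00 | 1.000 | 1.000 | .978 |
| Case 11, 1 year | .77 | .773 | .555 | .316 |
| Case 11, 3 years | .99 | .995 | .938 | .692 |

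The n = 333 column reproduces Table 1. If the one-year rates are simply tripled instead, Case 11 at three years is .823-.984 for n = 100-200. All values at 100-200 are upper bounds, because some rare patients will not be idiopathic.

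**The case against.** **Planning language.** Appendix D speaks in approximations, and Section VI calls its etiology shares informal. That excuses small differences. It does not cover 1000 patients with one disease against at most 600 with all rare diseases.

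**The size of the rare group.** A reader might infer that Section VI puts the rare etiologies at 35-40% of the Registry (2080-2380 of 6000). The document gives no such total. It does not say that its shares are primary diagnoses, and the Registry Baseline Form records concurrent etiologies (Q24) as well as one primary etiology (Q23.1). A diabetic or alcoholic case might also be ischemic. This objection stands: the firm comparison is 16.7% against at most 10%.

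**The clinic load.** It might also be inferred that centers face 104-119 Substudy visits each. Those are selections on the no-overlap sum and an example number of centers. The protocol gives no participation rate, so completed visits cannot be computed.

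**The strata.** Appendix D ends by naming its strata as ischemic and other, which could be read as sampling all hypertensive patients. Its own arithmetic points the other way, since the 7-13% is taken over the 5400-5700 ischemic or hypertensive patients. Section IX likewise describes a sample "to include ischemic and/or hypertensive heart disease, patients with idiopathic cardiomyopathy" and valvular disease, which need not be a rival sampling scheme. This is loose wording to tidy.

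**Later recruitment.** Section VIII extends recruitment of the rarer etiologies to June 1991. That can only add to the rare group. It does not reconcile two figures that both refer to 6000 patients.

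**Conclusion.** The contradiction is real, and nothing in the protocol resolves it. It needs no summing of categories: roughly 1000 idiopathic cases cannot fit inside a group of 300-600.

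On Section VI's count, full sampling of idiopathic cases alone uses all 1000 places. On Appendix D's count, Case 11 power is at most .316-.555 at one year (stated .77) and .692-.938 at three years (stated .99), and Case 10 one-year power is at most .656-.918 (stated .99). The three-year values rest on the assumed conversion of one-year rates.

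It would be too strong to say that the power of Cases 10-11 is lost altogether: Case 10 at three years stays at .978 or above. Nor is the primary objective at risk. All-cause mortality in the whole cohort depends neither on the Substudy fractions nor on this tertile comparison. The point should be fixed because the fractions go into an automated selection program and the power figures support the statement on study size.

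**What to change.** 1. Use one set of etiology prevalences in Section VI and Appendix D.
2. In Appendix D, define the strata by Registry Baseline Form Q23.1: ischemic or hypertensive, versus all other codes. Count valvular disease and active myocarditis in the expected size of the second stratum, since those codes fall there and are in none of the totals above.
3. Replace the fixed 100% with the smaller of 1 and R / N, where R is the number of places reserved for the second stratum and N its expected or early observed count. The sponsor chooses R so that the total stays near 1000 and an ischemic sample remains. As an illustration only, R = 600 keeps full sampling for any N up to 600. At N = 1000 it gives 600/1000 = 60% of the rare stratum and 400/5000 = 8% of the common one.
4. Restate Cases 10-11 of Table 1 with the reconciled idiopathic count.

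If early counts are to be used, the protocol must say so. The early estimate in Section IX serves only to develop a form for secondary cardiomyopathies; it is not a planned review of the sampling fractions.

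The cost is wording in two sections, two rows of Table 1 and one program parameter. If the fraction is updated during recruitment, the value in force at each selection must be kept. The real downside is that, if prevalence is high, not every rare case receives the Substudy tests, which departs from Appendix D's wish for complete data on these patients.
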